4.2. Medical History

Medical history will be coded to a Preferred Term (PT) and associated primary System Organ Class (SOC) according to the Medical Dictionary for Regulatory Activities (MedDRA[®]) version in effect and available at the time of the database lock.

4.3. Pre-Treatment / Concomitant Medication

Medications/Procedures will be recorded from the day of informed consent until the end of study (EOS) visit. Medications will be coded to the ATC level 2 (therapeutic main group) and ATC level 4 (chemical/therapeutic subgroup), according to the version of WHO Drug Dictionary (WHODD) in effect and available at the time of database lock. Note: a drug can be matched to more 1 ATC classification, ie, subjects can be counted in several categories for the same medication.

Pre-treatment medications/procedures: medications that were started prior to the first dose of the study drug or procedures performed prior to the first dose of the study drug.

Concomitant medications/procedures: medications taken (or continued to be taken) or procedures performed following the first dose of study drug through the end of the TEAE period (Section 4.7.1).

4.4. Prohibited Medication During Study

Definition of prohibited medications during the study is described in Section 5.6.1 of the study protocol.

All pre-treatment/concomitant medications will be reviewed to determine if any of them are prohibited medications on an ongoing basis throughout the study, with the final list to be finalized before database lock.

4.5. Exposure to Study Drug and Compliance Variables

Exposure to study drug variables are listed below with the associated definitions:

- The total number of study doses administered.
- The calculated actual dose (in the unit of mg/kg) of each study treatment. Actual dose is calculated as: (volume of dose × 150mg/mL) divided by body weight at dosing.
- Number of injections received for each dose.
- Length of observation period during the study is calculated as: (date of the last study visit - date of first dose of study drug) +1.

Compliance will be assessed using the following variables with the associated definitions applied to both REGN2222 and placebo:

- The compliance ratio (continuous) of actually administered dose (in the unit of mg/kg) vs. planned dose will be calculated for each dose received by a subject.

- The compliance ratio (categorical) defined above categorized into <0.8 , 0.8 to <1.2 , ≥ 1.2 , ≥ 1.5 , and ≥ 2.0 .

4.6. Efficacy Variable

Assessment of all efficacy variables will occur during the 150-day study period (ie, through the Day 150 visit). Any RSV infection occurring after that period will not be included in the efficacy evaluation.

For a subject who discontinued study treatment early (ie, not receiving the second dose), the subject will be followed to Day 150 visit for assessment of efficacy.

4.6.1. Primary Efficacy Variable

The primary efficacy variable is the proportion of FAS subjects with a medically attended RSV infection (hospitalization or outpatient LRTI) during the 150-day efficacy assessment period. The 150-day efficacy assessment period is defined as the first study drug administration through the Day 150 visit (defined as the protocol specified window which includes Study Day 155). In the event that Day 150 visit occurs beyond the protocol specified window (ie, on or after Day 156) and a respiratory AE is reported at that visit, that AE will only be considered for the primary endpoint if its start date is before Study Day 156.

A medically attended RSV infection (hereafter referred to as a primary endpoint event) is defined as an infant with a positive RSV test by RT PCR with any of the following events:

- Hospitalized (on the basis of the assessment of the admitting physician) for RSV infection.
- Outpatient visit (emergency room [ER], urgent care [UC], or pediatric clinic [PC] for either a sick or well visit) with RSV LRTI.

An RSV LRTI in an infant is defined as an RSV-proven respiratory infection (ie, positive RSV RT-PCR test) with parent(s)/guardian(s) report of cough or difficulty breathing, and with 1 of the following signs of LRTI, as assessed by a healthcare provider:

- Lower chest wall indrawing
- Hypoxemia (peripheral capillary oxygen saturation $<95\%$ breathing room air)
- Wheezing or crackles

The positive RSV RT-PCR test has to occur within a 14-day period since the start date of the adverse event (AE) corresponding to the medically attended respiratory illness (MARI), ie, the specimen collection date for RT-PCR - AE start date must be ≤ 14 . If multiple medical visits are made for the same episode of RSV illness, an RSV positive test by RT-PCR at any medical visit will label that episode as being RSV positive, and it will be counted toward the primary endpoint. If there are multiple medically attended visits during an episode associated with an RSV positive test, then the most severe occurrence will be defined as the primary endpoint event, and events of decreasing severity will be defined in the following order: RSV positive hospitalization $>$ RSV positive ER/UC LRTI $>$ RSV positive pediatric clinic LRTI. If a subject had multiple episodes of RSV infection, the first episode will be defined as the primary endpoint.

[figure not shown]
Only medically attended respiratory illness occurring during the 150-day efficacy assessment period will be considered for the primary endpoint. If categorization of a MARI event as an endpoint is unclear, source documentation will be provided to a blinded adjudication committee for categorization prior to database lock.

If an infant has a medically attended respiratory event but did not have an RT-PCR test conducted in the central laboratory within 14 days after onset of the episode of RSV illness, results from a RSV RT-PCR assay conducted in the local lab will be used to determine RSV infection if the RSV RT-PCR assay is reviewed by jurisdictional health authority and released for commercial distribution, or conducted in a laboratory that is currently certified for human diagnostic testing. To that end, protocol has specified the following conditions for acceptable local lab RSV RT-PCR assays:

- Assay is a FDA-cleared RSV RT-PCR assay or
- Assay is an RSV RT-PCR assay that is not FDA-cleared but is conducted in a laboratory that is currently CLIA (or equivalent) certified.

The algorithm to programmatically derive an observed primary endpoint event is depicted in [Figure 2](#).

Figure 2 Flow diagram to depict the programmatic derivation of an observed primary endpoint event

Answers to questions (1) through (7) in the flow diagram are collected from the following electronic case report form (eCRF) pages and other source data:

- Questions (1) and (3): eCRF page of “History of Medically-Attended Acute Respiratory Illness (MARI) Questionnaire”.
- Question (2): eCRF page of “Hospitalization for Respiratory Illness Questionnaire”.
- Question (4): eCRF page of “Lower Respiratory Infection (LRI) Questionnaire”.
- Questions (5): eCRF page of “Central Laboratory” for nose swab collection and eCRF page of “History of Medically-Attended Acute Respiratory Illness (MARI) Questionnaire” for AE start date.
- Question (6): Central lab RSV RT-PCR test results from Viracor.
- Questions (7) and (8): eCRF page of “Unscheduled RSV RT-PCR (Local Lab)”

On the eCRFs, the MARI questionnaire, the LRI questionnaire, and the central (or local) lab RSV PCR test(s) are designated by the investigator to a corresponding medically-attended acute respiratory adverse event (AE). Therefore, the corresponding AE serves as the key variable to programmatically merge information from the MARI and LRI pages with RSV PCR test(s) for each episode of illness.

Missing Data Handling for the Primary Efficacy Endpoint

For early termination (ET) subjects those who did not complete the 150-day efficacy assessment period, their primary endpoint will be handled according to the following rules in the primary analysis:

- Early termination subjects who had a primary endpoint event during the 150-day efficacy assessment period (regardless of treatment status, ie, whether the subject received all study drug doses or discontinued dosing) will be used in the primary analysis and included as “event occurred”. [Observed, thus no imputation]
- Direct imputation of missing primary endpoint at Day 150 visit:
 - Subject deaths prior to Day 150 that are adjudicated to be RSV related will be included as “event occurred” at the onset date of the adverse event that led to death.
 - Remaining early termination subjects (including non-RSV deaths) across all treatment groups, will be imputed to the average placebo score (estimated placebo event rate).
 - Approach to estimating the placebo event rate is the Kaplan-Meier (KM) estimate at Day 150 based on all randomized subjects in the placebo group. Early termination subjects in the placebo group who had no primary endpoint event will be censored in the KM procedure at the last time point when their primary endpoint event is assessed (ie, at the last visit completed by the subject, scheduled or unscheduled, prior to Day 150 visit). Placebo subjects who completed Day 150 visit with no primary endpoint event will be censored at the date of their Day 150 visit. The derivation of study day is detailed in Appendix 11.3.
- Imputed scores along with observed subject data will be utilized in the Cochran-Mantel-Haenszel (CMH) analysis.

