In Part B, assessment of the primary and secondary clinical endpoints (Section 8.2 and Section 8.3 for endpoints) will only occur during the 150 day study period. Any RSV infection occurring after Day 150 will not be included in the efficacy evaluation. If a primary endpoint is reached during the study period (Section 8.2), ongoing assessments for other endpoints and measurements will continue until the end of the study period. Any subject who has had a positive RT-PCR RSV nasal swab result, either at the study central laboratory or at an outside institution in a Clinical Laboratory Improvement Amendments (CLIA)-certified (or equivalent) laboratory, should not receive a second dose of study drug. The risk of a second RSV infection is substantially (~70%) reduced for 6 months after the first infection and this practice is consistent with recommendations in the 2014 AAP guidelines for palivizumab prophylaxis (Ohuma 2012). Subjects who have reached the primary endpoint will continue to be monitored for additional medically attended acute respiratory infections that may occur during the study period.

All subjects will be monitored for safety until the end of the study at Day 237. Safety monitoring after Day 150 through Day 237 (end of study) will be made by telephone call, only to solicit information about concomitant medications and AEs. In order to minimize total blood samples obtained throughout the study, a sparse blood collection schedule will be implemented based on a blood collection schedule that includes up to 3 total planned blood draws for each infant for safety laboratory tests, PK, and ADA assays. The schedules of events are provided in Section 6.1. Subjects who complete Day 150 may be eligible to enroll in a subsequent extension study in which they will be monitored for medically attended episodes of wheezing over a 12-month period.

The end of study will be approximately 180 days after the last dose or approximately 237 days after the first dose, whichever is longer.

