Study site personnel will evaluate the subject during an unscheduled visit as soon as possible or within 72 hours after receipt of medical attention. Evaluation will include a history of the acute illness and nose swab collections for viral detection will occur. All nose swabs will be tested using a reverse-transcriptase polymerase chain reaction (RT-PCR) assay for RSV, which will be conducted in a central laboratory. All RSV isolates will be subtyped. If the unscheduled study visit following a medically attended respiratory infection occurs >72 hours but <14 days of discharge from the medical facility, all procedures (as appropriate), including nose swab collection, should occur despite being outside of the 72 hour window. If the child has had an RSV-confirmed medically attended visit, nose swab collection will be required at the unscheduled study visit. Unscheduled study visits for medically attended respiratory illness will be required through Day 150 even if a child has had a prior RSV-confirmed or other respiratory illness. Unscheduled study visits for medically attended respiratory illness will not be required between Day 151 and Day 237 (end of study) for the purpose of nose swab collection.

A new Medical Information Packet will be provided to the parent(s) or guardian(s) following each potential medically attended respiratory illness visit.

For infants who do not have an RSV RT-PCR assay for RSV infection done by the central laboratory, study site personnel will obtain and record information about all RSV RT-PCR assay done in a medical facility, including result(s), name of the assay(s) and whether the laboratory(ies) conducting the RT-PCR is a CLIA (Clinical Laboratory Improvement Amendments) certified (or equivalent) laboratory.

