Administer Study Drug 		$X^5$		X 								
Concomitant Medications and Procedures	X	X	X	X	X	X	X	X	X	X		
Vital Signs 	X	X	X	X	X	X	X					
Physical Examination (including weight)	X	X 	X	X 	X		X					
Adverse Events 	X	X 	X 	X 	X 	X 	X 	X 	X 	X 		
Blood Sampling	·			•								
Hematology	X 		X 	X 	X 	X 	X 					
Blood Chemistry	X 		$X^{10}$	X 	X 	X 	X 					
Pharmacokinetics			$X^{10}$	X 	$X^{12}$	X 	X 					
Anti-REGN2222 (ADA)	X 		$X^{10}$	X 	$X^{\setminus 12}$	X 	X 					

Study Periods	SV 	BV	Treatment Period		Postdose Follow-Up						
Visit	1	2	3	4	5	6	7/ET	8 	9 	10/EOS 	
Day	-28 to -1	1	29±2	57±2	85±5	113±5	150±5	178±10	206±10	237±10	
Optional Substudy Informed Consent	X										
Optional DNA Sample		X 									
Pharmacoeconomic Information 		X	X	X	X	X	X				
Risk Factors Assessment		X									

ADA=antidrug antibody; BV=baseline visit, EOS/ET=end of study/early termination; IM=intramuscular; SV=screening visit; X=all subjects unless otherwise specified

- 1. All safety assessments performed at screening must be normal and checked against the inclusion/exclusion criteria before REGN2222 administration on Day 1(baseline)
- 2. Subject randomization and blood collection schedules are assigned using the interactive voice response system (or interactive web response system) at Visit 2. Depending on the availability of the study pharmacist or designee, subjects may be randomly assigned on Day -1 or Day 1.
- 3. When parent(s) or guardian(s) take their child for medical attention outside of the study site, the parents/guardians are instructed to take the Medical Information Packet with them for use by their healthcare provider. Data on medically attended RSV infections will be collected for all subjects until Day 150.

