Results from non-RT-PCR RSV assays will not be collected. Only medically attended respiratory visits occurring during the first 150-day period will be counted toward the primary endpoint.

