2.3. Study Plan

After the parent(s) or legal guardian(s) provide informed consent (obtained up to 28 days prior to randomization), subjects will be assessed for study eligibility for Part B at the screening visit. Subjects who continue to meet eligibility criteria at baseline will undergo Day 1 baseline assessments and will be randomly assigned in a 1:1:1 ratio to REGN2222 30 mg/kg single dose (1 dose REGN2222 and 1 dose placebo), REGN2222 30 mg/kg Q8 weeks (2 doses of REGN2222), or placebo (2 doses of placebo). The study flow diagram for Part B is depicted in Figure 1.

Figure 1: Part B: 30 mg/kg IM (1 Dose REGN2222 and 1 Dose Placebo), 30 mg/kg IM (2 Doses of REGN2222), or Placebo IM (2 Doses of Placebo)

EOS = end of study; IM = intramuscular; Q8 = every 8

Note: The screening visit occurs from Day -28 to Day -1. Black arrows denote dosing visits. Subjects will be monitored on site for at least 1 hour after each dose of REGN2222 or placebo. Grey arrows denote study visits at which dosing does not occur. Visits 8, 9, and 10 will occur via phone call. In the event an AE is reported during a phone call visit, an unscheduled onsite visit may be required to follow-up, per investigator.

In Part B, assessment of the clinical efficacy endpoints will only occur during the 150 day study period (ie, through Visit 7). Any RSV infection occurring after Day 150 visit will not be included in the efficacy evaluation. If a primary endpoint is reached during the study period, ongoing assessments for other endpoints and measurements will continue until the end of the study period. Subjects who reach the primary endpoint during the study period will not have additional study drug administered for the remainder of the RSV season because the risk of a second RSV infection is substantially (~70%) reduced for 6 months after the first infection (Ohuma 2012) and this practice is consistent with recommendations in the 2014 AAP guidelines for palivizumab. Subjects who have reached the primary endpoint will continue to be monitored for additional medically attended acute respiratory infections that may occur during the study period.

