During the 150-day efficacy assessment period, data will be collected on subjects with any acute respiratory illness requiring medical attention. After enrollment of their infant into the study, parent(s) or guardian(s) taking their enrolled infant to a healthcare provider (inpatient or outpatient, including hospitalizations, ER, UC, or pediatric clinic) will be asked to contact the study staff immediately or soon after seeking medical attention for any of the following symptoms: fever, cough, earache, nasal congestion, rhinorrhea, vomiting after coughing, wheezing, or difficulty breathing (labored, rapid, or shallow).

When the parent(s) or guardian(s) takes their child for medical attention for an acute respiratory infection, they will be instructed to take a Medical Information Packet with them for the treating clinician. All infants who have a medically attended visit for a respiratory illness will be asked to have an unscheduled study visit as soon as possible or within 72 hours of discharge from the medical facility. Study site personnel will evaluate the subject during an unscheduled visit, including a history of the acute illness and nose swab collections for viral detection will occur. All nose swabs will be tested using a reverse-transcriptase polymerase chain reaction (RT-PCR) assay for RSV, which will be conducted in a central laboratory. All RSV isolates will be tested for their subtypes, specifically subtype A or subtype B. If the unscheduled study visit following a medically attended respiratory infection occurs >72 hours but <14 days of discharge from the medical facility, all procedures (as appropriate), including nose swab collection, should occur despite being outside of the 72 hour window. Unscheduled study visits for medically attended respiratory illness will be required through Day 150 even if a child has had a prior RSV-confirmed or other respiratory illness. Unscheduled study visits for medically attended respiratory illness will not be required between the day after the Day 150 visit and Day 237 (end of study) visit for the purpose of nose swab collection.

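### The primary endpoint has two end dates, Day 150 and a visit window running to Day 155, and a late RSV-positive PCR can put an infant in the non-RSV group

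*SAP*

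**What the plan says.** **End of counting, protocol.** Section 3.1.2.3: "Any RSV infection occurring after Day 150 will not be included in the efficacy evaluation". Section 8.2 (Part B): "Only medically attended respiratory visits occurring during the first 150-day period will be counted toward the primary endpoint". Section 3.1.2.4: "Unscheduled study visits for medically attended respiratory illness will not be required between Day 151 and Day 237 (end of study"). Table 2, footnote 3 (Section 6.1): "Data on medically attended RSV infections will be collected for all subjects until Day 150". Section 9 uses the visit instead. Section 9.5.2.1 defines early termination as not completing the Day 150 visit, and 9.5.6.1 treats Part B Visit 7 as the end of the efficacy period. Section 6.2.2.7 schedules that visit at Day 150±5.

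**End of counting, SAP.** Section 4.6.1 counts from first dose "through the Day 150 visit (defined as the protocol specified window which includes Study Day 155"). For a Visit 7 on or after Day 156 at which a respiratory AE is reported, "that AE will only be considered for the primary endpoint if its start date is before Study Day 156". Section 2.3 restates the two protocol sentences with the word visit added: "Any RSV infection occurring after Day 150 visit will not be included in the efficacy evaluation", and unscheduled visits "will not be required between the day after the Day 150 visit and Day 237 (end of study) visit". Section 4.6 also runs efficacy through the visit. The SAP's copy of Table 2, footnote 3 (Appendix 11.2) keeps Day 150. The placebo rate used for imputation is the Kaplan-Meier estimate at Day 150.

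**PCR window.** SAP 4.6.1 and Note 1 of 4.6.3 accept a positive RT-PCR only if the specimen was taken within 14 days of AE onset. Protocol 3.1.2.4 and 6.2.3 ask for a swab within 72 hours of discharge, and still call for one up to about 14 days after discharge. SAP 5.7.5.3 classes a hospitalization or outpatient LRTI as non-RSV when results within 14 days of AE onset are all negative or missing. SAP 5.12 uses that group for the multiplex panel summary.

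**The concern.** SAP 4.6.1 derives the endpoint by program, so the written dates decide who is a case. The secondary endpoint inherits them (SAP 4.6.2).

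- With two end dates, illness on Days 151-155 can count although the protocol no longer requires a swab visit then. Capture in those days may be incomplete.
- SAP 4.6.1 does not settle whether an infant seen on Days 145-154 is counted to that visit or to Day 155. Two programmers could derive different cases.
- For late visits the SAP limits the AE start date, whereas protocol 8.2 counts medical visits.
- Observed events can run to Day 155 while the imputed rate stops at Day 150.

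The PCR rule raises a different problem. A swab taken when the protocol allows can be too late to count, and the infant is then reported as having a non-RSV illness despite a positive RSV PCR.

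**Working it through.** **Inputs.** Placebo rate 10%, active rate 4%, 5% early dropout, 505 per arm originally and about 1200 in total now (protocol 9.2); Visit 7 at Days 145-155 (protocol 6.2.2.7). Assumption: constant hazard to Day 150, continuing to Day 155.

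**The plan's own figure.** 505 × (0.10 + 0.04 + 0.04) = 90.9, against the stated total of about 90 events. For 400 per arm: 400 × 0.10 + 800 × 0.04 = 72.

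**Events on Days 151-155, every infant seen on Day 155.** Daily hazard h = -ln(1 - p)/150.
- Placebo: 400 × 0.90 × (1 - exp(-5h)) = 1.26.
- Both active arms: 800 × 0.96 × (1 - exp(-5h)) = 1.04.
- Total about 2.3, or 3.2% of 72. Linear check: 72 × 5/150 = 2.4.

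**Visits spread evenly over Days 145 to 155.** Mean time beyond Day 150 is (1+2+3+4+5)/11 = 1.36 days, giving about 0.63 events (0.34 placebo), or 0.9% of 72.

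**If the hazard in those days differs (assumed range).**

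| Hazard in Days 151-155 | All seen Day 155 | Evenly spread |
|---|---|---|
| half | 1.2 | 0.3 |
| same | 2.3 | 0.6 |
| double | 4.6 | 1.3 |

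**Effect on the comparison.** At constant hazard the cumulative rates at Day 155 are 10.316% and 4.131%. Their ratio is 4.131/10.316 = 0.400, the same as 4/10 at Day 150.

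**Effect on imputation.** With 5% of 400, or 20, early terminations in an arm, moving the imputed rate from Day 150 to Day 155 changes the imputed count by 20 × (0.1032 - 0.1000) = 0.06 events.

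**PCR window.** If discharge comes k days after onset, the latest permitted swab is about k + 14 days after onset. The documents give no onset-to-discharge times, so k is assumed: for k = 3, 7 and 10 the latest swab falls on day 17, 21 and 24, all beyond the SAP's 14. A swab taken within 72 hours fails only if k + 3 > 14, that is, k > 11.

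Take an infant with a hospitalization or outpatient LRTI whose only PCR is a positive specimen after day 14.
- SAP 4.6.1: no qualifying positive, so not a case.
- SAP 5.7.5.3: results within 14 days of onset are missing, so non-RSV. That section excludes only infants who also had a primary endpoint event, which this infant did not.
- With an early negative swab as well, the class depends on whether the 14-day limit in 5.7.5.3 also governs the all-negative condition. The text can be read either way.
- SAP 5.12: the panel is run only on swabs negative on the central RSV assay (SAP 4.12), so only an infant who also has a negative swab can reach that table.

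**The case against.** The best defence is that protocol Section 9 already uses Visit 7 as the end of the period, so the SAP follows the protocol's statistical section. That stands in part: the conflict is partly inside the protocol. It does not remove it, because 9.5.2.1 says who completed and 9.5.6.1 sets the data cut-off, while 3.1.2.3 and 8.2 say what counts.

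A second defence is that a study-site visit is itself a qualifying outpatient visit. A strict Day 150 limit would then drop an RSV LRTI found at an in-window Visit 7 on Days 151-155. That stands, and it is the reason to keep the Day 155 rule as a sensitivity analysis.

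For late visits, SAP 4.6.1 also limits events in general to illness within the period. That narrows the gap but is not a visit-date rule. On the PCR window, some late positives may be new infections, which supports keeping the onset-based limit as the primary rule.

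A reader might infer more than the documents support:
- **An undisclosed change, because SAP 1.2.3 lists no modifications.** That heading covers only the protocol's statistical section, which already refers to the visit.
- **Counting time that certainly differs by 10 days between infants.** This is one reading; a common Day 155 limit is another.
- **A non-RSV group and panel summary that are widely wrong.** SAP 5.7.5.3 is exploratory, descriptive and limited to hospitalization or outpatient LRTI. SAP 5.12 is reached only as described above.
- **Doubt about local specimens.** Note 1 of SAP 4.6.3 is not restricted to central-laboratory tests.
- **Bias.** The rules are the same in every arm, and none is shown.

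**Conclusion.** The point holds and is minor. The two documents give different end dates for the primary endpoint, and the SAP text does not resolve how its own window works for infants seen before Day 155. At the design rates and a constant hazard, the days in dispute carry about 0.6 of 72 expected events with evenly spread visits and about 2.3 if all infants are seen on Day 155. The relative effect and the imputation are practically unchanged. The hazard late in follow-up is an assumption.

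The non-RSV classification is wrong for an infant whose only PCR is a late positive. It affects an exploratory summary, in a number of infants that cannot be estimated from the documents.

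**What to change.** (a) Reconcile protocol 3.1.2.3, 3.1.2.4, 8.2, 9.5.2.1 and 9.5.6.1 with SAP 2.3, 4.6 and 4.6.1. State one common cut-off in SAP 4.6.1 and 4.6.2: date of the medically attended visit, through Study Day 150, as protocol 8.2 has it. Keep infants with Visit 7 on Days 145-149 as completers and count any recorded qualifying visit through Day 150. For the Kaplan-Meier estimate, use the same events and censor event-free completers at the earlier of their last assessment and Day 150, so that unassessed days are not treated as event-free. Keep the SAP's Day 155 rule as a sensitivity analysis.

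(b) In SAP 5.7.5.3, and so in 5.12, exclude any infant with a positive RSV RT-PCR linked to that illness, whatever the day of the swab.

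(c) Keep the onset-based PCR window as the primary rule. Add a sensitivity analysis that counts any positive RSV RT-PCR linked to the same AE and collected within the protocol's permitted swab period.

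The cost is SAP wording, derivation code and two extra tables before database lock. AE start and swab collection information is on the eCRF pages named in SAP 4.6.1, and tests are already linked to the AE. I assume that medical-visit dates are recorded too; the documents do not list the fields. The primary count would lose about one or two expected events at most at a constant hazard.
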